Each patient's GFR will be recorded prior to the exams and 48-72 hours after scanning. In addition, each patient will be contacted at baseline as well as 6 weeks, 3 months, and 6 months post-scan to comprehensively evaluate for any symptoms or signs of NSF (see attached sheet) [19]. If at any point a patient's follow-up interviews indicate they might be experiencing symptoms of NSF, or if their post-MRI research blood draw indicates deteriorating renal function, the study PI will be notified and the patient will be referred for further medical evaluation, if necessary. All relevant demographics, such as hypertension, diabetes, coronary artery disease, and liver disease, will be recorded. The data will be analyzed, using standard statistical methods, for any significant and disparate variations in renal function.

Aim 2:

Each MRI exam will be independently interpreted by 2 participating sub-specialty-trained (either neuro or body) radiologists. To limit bias, the readers will initially be blinded to history and prior exams and their respective interpretations recorded in the research database (history and prior exams will subsequently be provided, as usual, for the final interpretations used in clinical care). The interpretations and inter-reader correlation will be recorded for each exam. Via Loyola electronic medical record (EMR) we will record the chronology of all subsequent related diagnoses, imaging studies, pathology results, therapies, and related costs (defined as gross hospital charge), within the study period (1-2 years) and for one year afterward. These data will be analyzed to compare differential outcomes between the non-contrast and contrast cohorts.

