To further explore the concept of Gadoterate-based differential outcomes, two separate interpretations for each Gadoterate-enhanced MRI will be recorded in the research database: an interpretation based upon only the non-contrast images and the full interpretation of the whole exam (non-contrast + contrast images). We will subsequently record the *predicted* outcome data, as described above (diagnoses, subsequent imaging studies, pathology results, therapies, and projected related costs), that would be associated with the more limited interpretation of the non-contrast images. Comparison to the actual outcomes of that patient will subsequently be analyzed. This is both feasible and straightforward since the vast majority of the clinical MRI indications in this study have a well-defined diagnostic/therapeutic pathway – i.e. a solitary liver lesion demonstrated to be malignant by contrast MRI would result in chemo-embolization, whereas an indeterminate result based on non-contrast would lead to a liver biopsy [18]. Another example: Cystic renal lesions which cannot be completely characterized without contrast are typically followed with serial imaging exams to check for growth, whereas demonstration of a simple cyst by contrast-enhanced exam will typically result in no further imaging.

Statistics:

Previously-tested GBCAs in chronic kidney failure patients have resulted in 10-25% rates of decreased GFR, depending upon the study, with most investigations recording rates in the range of ~15% [5]. Based upon various data thus far (noted above), the rate is expected to be no more than 5% using Gadoterate;

therefore if we wish to detect a significantly lower rate of renal complications with a power of 90% and a 5% significance, then a sample size of approximately 136 patients receiving Gadoterate is properly powered to address Aim 1. The non-Gadoterate control arm does not need to be as large for analysis of Aim 1, however, it will consist of 136 patients as well, to properly power analysis of Aim 2. This number is expected to be more than sufficient considering that significant interpretive and outcome differentials are anticipated at a far greater rate than 5%, between the non-contrast image and contrast image evaluations.

Study Procedures

Subject selection

Inclusion Criteria: GFR less than 30 ml/min, but not on dialysis, with indications for MRI as described above. GFR will be calculated in the same fashion as in current use in our department:

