$$\text{eGFR} = \frac{(140 - \text{Age}) \times \text{Mass (kg)} \times (0.89 \text{ if female})}{72 \times \text{serum creatinine (mg/dL)}}$$

Exclusion Criteria: Pregnant and lactating females; planned initiation of chemotherapy or surgery within 72 hours of the MRI exam; hemodynamic instability or acute coronary syndrome; history of the following nephrotoxic medications within 2 weeks of the exam: Amphotericin B, Lithium, Pentamidine, Aminoglycosides, Acyclovir, Gancyclovir, or Foscavir; age less than 18 years.

Note that many patients within the inclusion criteria may have pre-existing conditions which could, theoretically, cause a GFR decrease unrelated to the Gadoterate in the 48-72 hour post-injection window; however, such cases will be statistically represented in both cohorts and, as such, are not expected to affect the comparisons between the two populations due to the sufficient statistical power of the study.

Recruitment

Patient recruitment will occur via two complementary mechanisms: In the clinician office when the study is ordered and via the research nurse and/or study coordinator. It is expected that a significant component of patients will be recruited into the study by the clinicians in the participating departments. Education of clinicians in these departments is ongoing at this time and all have been enthusiastic about participating. In addition, the nurse coordinator will review the radiology informatics system, on a daily basis, to identify all eligible patients for whom non-contrast MRIs have been ordered due to GFR concerns. In such cases the nurse coordinator will contact the study PI to determine eligibility. If the patient meets eligibility criteria, the study PI will confirm with the patient's ordering physician. The patient will be contacted and the study PI, sub-investigator, or other appropriate study staff will explain the study, with its risks and benefits, to the patient at least 8 hours prior to the MRI exam. The study PI or sub-investigator will contact the ordering physician prior to the date of the exam to obtain an updated order allowing for contrast MRI. Signature of the consent form itself will then be available for the patient at the time of the exam. In either of these scenarios a patient who does not want Gadoterate contrast will receive the usual non-contrast MRI.

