In reviewing the radiology informatics system, the coordinator may identify a patient who meets eligibility criteria and whose GFR has already been obtained through standard care, but who already had a standard MRI completed without contrast within the past 24 hours. If this occurs, the PI will be notified to determine if it is appropriate to contact the patient and obtain consent post-MRI. If the patient consents

to the study, they would be placed into the control (non-contrast) group and undergo the remaining study activities of post-MRI blood draw and questionnaires at baseline, 6 weeks, 3 months and 6 months.

Consent

A discussion of the study, including discussion of risks and benefits, will be conducted by the study staff (PI, sub-investigator, research nurse, or study coordinator) with the patient at least 8 hours prior to the exam (except, as noted above, in the event a patient is identified post-exam). The consent form can then be signed at the time of the exam. Consent will be obtained following our institution's policies and procedures. Patient eligibility will be confirmed prior to study enrollment.

If a patient is unable to give informed consent due to cognitive dysfunction (for example, stroke, trauma, or encephalopathy from liver failure), their guardian, spouse, parent, or the individual holding power of attorney for their healthcare will be approached to consent for the patient. If the patient regains his or her ability to make decisions, he or she will be informed about the study and asked for a decision about continued participation. In the event the patient does not regain his or her ability to make decisions at the time the questionnaires are administered, the individual who consented on behalf of the patient will be asked to answer the symptom questionnaires on the patient's behalf.

Recruitment materials

No advertising will be provided. Written material will consist of the ICD. \$25 will be provided to patients as compensation for their 2-3 day return visit (blood-draw) and \$5 for parking.

Selection

It is expected that a significant percentage of patients fulfilling the eligibility criteria will nevertheless choose to decline receiving Gadoterate and receive the default non-contrast exam. These patients will be asked to take part as the non-contrast arm of the study.

Gadoterate

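### The protocol relies on representation in both cohorts and on statistical power to keep pre-existing conditions from distorting the 48-72 hour renal comparison, but power does not remove confounding between non-randomised cohorts and no adjustment is named

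*Combined protocol and SAP*

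**What the plan says.** The note after the exclusion criteria (Study Procedures, Subject selection) concedes that many eligible patients may have conditions that could "cause a GFR decrease unrelated to the Gadoterate in the 48-72 hour post-injection window". It then gives two reasons for setting this aside: "such cases will be statistically represented in both cohorts", and these cases "are not expected to affect the comparisons between the two populations due to the sufficient statistical power of the study".

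Cohort membership is described elsewhere. Under Selection, eligible patients who decline Gadoterate supply the controls: "These patients will be asked to take part as the non-contrast arm of the study". Under Recruitment, a patient found within 24 hours after a non-contrast MRI may consent afterwards, in which case "they would be placed into the control (non-contrast) group". Randomisation, matching and stratification are not mentioned.

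On analysis, Study Design, Aim 1 has GFR measured before and 48-72 hours after the scan, and states: "All relevant demographics, such as hypertension, diabetes, coronary artery disease, and liver disease, will be recorded". The renal data are then to be examined by standard methods that are not named. Specific Aim 1 mentions analytic models without saying what they contain.

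**The concern.** Both reasons in the note fail as safeguards. If representation means only that such patients occur in each cohort, that is not balance. If it means that they occur in similar proportions, the design offers no support for it, because patients choose their cohort or enter the control group after the event. Power is the wrong tool on either reading: a larger sample estimates a biased difference more precisely.

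What is at stake is the cohort comparison of early renal decline. If controls carry more background risk, a real harm can be hidden. If the Gadoterate cohort carries more, a harm can appear that contrast did not cause. The study is a single-site pilot meant to lead to a larger trial, and renal toxicity is the reaction it specifically monitors.

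**Working it through.** **1. What the stated power refers to.** Statistics gives about 15% for earlier agents, at most 5% for Gadoterate, 90% power, 5% significance and 136 patients. The formula and the number of sides are not stated. A one-sample calculation against a fixed 15%, two-sided, with the null variance, gives

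n = (1.960 + 1.282)² × 0.15 × 0.85 / 0.10² = 134,

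which is close to 136. Two-sample calculations at 90% power with equal cohorts give 178 to 207 two-sided and 145 to 172 one-sided. The 136 therefore fits a comparison with an external rate. That agrees with the protocol's remark that the control arm need not be as large for Aim 1. For 136 against 136 at 15% v 5%, power is 78.8% two-sided. So the power that the note invokes does not appear to belong to the cohort comparison. Even if it did, step 2 would still apply.

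**2. Does power protect against imbalance?** The documents give no background rate of decline without contrast and no prevalence of the conditions, so every input here is assumed: no drug effect, and a high-risk share of 50% in controls and 40%, 30% or 20% in the Gadoterate cohort. Low/high risks of decline are 5%/15% or 5%/25%.

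Cohort rate = low risk + (high risk − low risk) × high-risk share. For example, with 5%/25% and a 30% share: 5% + 20% × 0.30 = 11%. Controls: 5% + 20% × 0.50 = 15%. Bias = −4 points.

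The rejection rates below enumerate all outcomes of two independent binomials, using the two-sided Pearson chi-square at 5% without continuity correction.

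| Risks | Share, Gadoterate v control | Rates | Bias (points) | False significance, 136 per cohort | 272 per cohort |
|---|---|---|---|---|---|
| 5%/15% | 50% v 50% | 10% v 10% | 0 | 5.1% | 5.0% |
| 5%/15% | 40% v 50% | 9% v 10% | −1 | 6.0% | 6.8% |
| 5%/15% | 30% v 50% | 8% v 10% | −2 | 9.0% | 12.8% |
| 5%/15% | 20% v 50% | 7% v 10% | −3 | 14.5% | 24.1% |
| 5%/25% | 50% v 50% | 15% v 15% | 0 | 5.0% | 4.9% |
| 5%/25% | 40% v 50% | 13% v 15% | −2 | 7.5% | 10.2% |
| 5%/25% | 30% v 50% | 11% v 15% | −4 | 16.4% | 28.1% |
| 5%/25% | 20% v 50% | 9% v 15% | −6 | 33.1% | 57.8% |

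High-risk patients are present in both cohorts in every row; even at 20% v 50% there are about 27 and 68 of 136. Doubling the cohorts leaves the bias unchanged and, wherever there is imbalance, raises the error rate. Swapping the cohorts reverses the sign.

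**3. Masking.** Suppose that Gadoterate truly adds 10 points, with 136 per cohort. The chance of a significant result in the harm direction falls from 64% with balance to 48% at 30% v 50% (risks 5%/15%), and from 55% to 25% (risks 5%/25%).

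**4. Does adjustment help?** A two-stratum Mantel-Haenszel test on the same factor, assumed to be measured without error, was simulated at 136 per cohort. False significance returns to about 5%. In the step 3 cases, the chance of finding the harm returns to about 66% and 58%.

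**The case against.** Several points on the other side stand.

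- *The powered renal claim is elsewhere.* It sets the Gadoterate cohort against an external rate of about 15% and does not depend on cohort balance. A reader might infer that the main safety conclusion is undermined. It is not, at least by this point. What is exposed is the cohort comparison that Aim 1 and the note also describe.
- *Differences are partly limited.* Each patient's later GFR is read against their own baseline, and all share the exclusions and the entry limit "GFR less than 30 ml/min, but not on dialysis". This narrows differences in GFR level. It does not equalise the risk of decline from diabetes, heart disease or liver disease.
- *Adjustment is not ruled out.* The analytic models and standard methods could include it. A reader might infer that the plan has decided against adjusting; the text does not say so. It names no adjustment, and its note treats the problem as already handled.
- *The physician's part in allocation.* For patients found by the coordinator, an investigator "will contact the ordering physician prior to the date of the exam to obtain an updated order allowing for contrast MRI". A reader might infer that patients refused contrast by their physician become controls. No section says this; such patients may simply not enter the study.
- *The illustration rests on assumed inputs.* That is correct, and at the mild end the effect is small: 6.0% against 5.1%.

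**Conclusion.** The concern holds for the between-cohort renal comparison. The power argument is wrong in principle, and the representation argument is at best an unsupported assumption given how controls are obtained. This is more than missing detail, because the plan offers a safeguard that does not work.

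Size and direction cannot be known from the documents. Under the assumed inputs the effect runs from negligible to large. A reader might infer that the bias must favour Gadoterate, but nothing shows which patients decline or are consented after their scan. Nor does the point extend to the within-patient comparison in Aim 2. The between-cohort part of Aim 2 has similarly formed groups, but the note makes no claim about it; there the only gap is that no adjustment is stated. The point should be fixed, but it does not invalidate the study.

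**What to change.** Delete the statement that representation and power protect the comparison. Pre-specify that the between-cohort renal comparison is adjusted for baseline variables already recorded or available: baseline GFR, age, diabetes, hypertension, coronary disease and liver disease. Events will be few (136 × 5% = 6.8; 136 × 15% = 20.4), so name a method suited to that, such as a propensity score or stratification. Report a baseline balance table, and describe the result as a non-randomised comparison that may still be confounded.

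The cost is a few sentences, a little more analysis and some precision; no new patients or procedures are needed. The loss of precision grows with the imbalance. Assume a normally distributed logit propensity with SD 0.5, 1.0 or 1.5 (c-statistic about 0.64, 0.74 or 0.81), a known score and constant outcome variance. Inverse-probability weights then widen intervals by √[(1 + exp(SD²/2))/2] = 1.033, 1.151 or 1.428, that is about 3%, 15% or 43%. Overlap weights widen them by about 3%, 10% or 19% (by simulation). Unmeasured confounding remains.

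Optional, and not part of the error: the same adjustment for the between-cohort Aim 2 comparison, and a sensitivity analysis without controls consented after their scan.

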of contrast administration can never be entirely ignored, it is important to be cognizant of these conclusions when considering the suboptimal clinical care often afforded patients who do not receive Gadolinium contrast exams. For example, definitive diagnosis of hepatocellular carcinoma in a patient with cirrhosis, or of renal cell carcinoma in a patient with uncharacterized renal lesions, is all but limited to contrast-enhanced imaging, and manifests in dramatically disparate therapy compared with less definitive diagnosis (therapy initiation vs. serial follow-up imaging or invasive biopsy). Therefore, the benefits of having a GBCA on formulary, with which Gadolinium-enhanced MRI exams could be performed on any patient, regardless of GFR, would be significant to patient-care. The potential scale is significant due to the number of patients that fall into this category in our institution's catchment population as well as across the U.S. [17]. However, widespread misunderstanding of the chemical and clinical data has instilled fear of both medical and legal complications and has precluded current radiology practices from using GBCAs in patients with GFR<30. Currently, we estimate in excess of 800 exams that are annually performed at our institution without Gadolinium enhancement – and thus suboptimally - due to GFR restrictions. Our goal is to therefore gather robust single-site pilot data at Loyola University Medical Center and then proceed to a larger multi-site trial demonstrating the safety and utility of Gadoterate in this particular patient population.

Hypothesis and Study Aims

Hypothesis 1: Use of Gadoterate in a population of patients with GFR<30 will not result in statistically-significant numbers of adverse renal events, defined by decreased GFR and/or NSF.

Hypothesis 2: Use of Gadoterate in a population of patients with GFR<30 will result in more definitive radiologic interpretations and improved clinical care compared with those associated with non-contrast images only. Metrics of evaluation include improved timeliness and quality of disease treatment, as well as fewer follow-up imaging studies with greater specificity (see below).

Specific Aim 1: Establish Gadoterate-based MRI protocols for GFR<30 patients, and establish database (and analytic models) of pre and post-exam laboratory data as well as relevant demographic data.

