Gadoterate will be the only contrast agent used. There is no placebo and no blinding is needed. Gadoterate will be provided by Guerbet pharmaceuticals and will be stored in the identical fashion that all Gadolinium agents are stored in the department (see attached package insert). Gadoterate will be administered according to its standard weight-based protocol, 0.2 mL/kg [8].

Administrative Organization

This will be a single site study conducted at Loyola University Medical Center. Patient recruitment and participation from the referring clinicians in the hepatology, neurosurgery, neurology, neurosurgery, and urology divisions will be coordinated by an MRI nurse coordinator, who will devote 10% time to this project. In addition, all blood draws and patient follow up will be coordinated by the nurse coordinator. All imaging will be conducted on-site. The standard LUMC laboratory locations and procedures will be used to calculate GFR from the patients' serum.

The clinical research office (CRO) will assist with statistical data analysis.

Safety and Monitoring

As with any intravenous contrast agent, numerous nonspecific adverse (mostly allergic-type) reactions are possible, though rare (see attached package insert), for Gadoterate, and no more common than in any other agent in clinical use. The most serious adverse event is difficulty breathing. Patient safety related to

such events will be monitored by direct technician and nurse supervision at the time of the exam and in the immediate period following – this is standard department protocol for all contrast MRI exams.

The main additional serious adverse reaction is the one being specifically monitored in this study - renal toxicity. Monitoring of this will be done by 48-72 hour post-exam serum creatinine evaluation, as described above. In addition, long-term toxicity in the form of NSF will be evaluated by detailed phone follow-up, designed to identify any potential signs of NSF (see Figure 2). In the event of a positive response to 3 or more of the questions in the questionnaire, the patient will be assisted in scheduling a Dermatology appointment at LUMC.

The PI ([name]) and the nurse coordinator will be responsible for tracking and assessing any adverse events.

Reporting of Adverse Events or Unanticipated Problems involving Risk to Participants or Others:

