The risks particular to involving this patient population (GFR < 30 ml/min) in this trial are decreased renal function, including the possibility of the need for permanent dialysis, and NSF. However, extensive clinical experience and literature clearly support the fact that the chance of significant renal dysfunction is small and the chance of NSF is quite remote. On the other hand, the addition of Gadolinium contrast to an MRI exam is often of critical importance for determining accurate anatomic relationships, differentiating benign from malignant lesions or infected tissue from normal tissue, and determining resolving vs.

worsening disease. Patients who are ill and who therefore often need these important determinations from their MRI studies are often the ones unable to have Gadolinium contrast due to GFR concerns. Thus, while the risk is real, the benefits are clear and of immediate impact in numerous clinical situations. It is anticipated that patients involved in this study will be the recipients of such benefits. More generally, establishment of safe contrast-MRI protocols in this general population will contribute to advancement in the standard of care by which MRI is utilized for them, with these benefits potentially realized on a much more significant scale.

References

- [1] Thomsen HS: Nephrogenic systemic fibrosis: A serious late adverse reaction to gadodiamide. *Eur Radiol* 16: 2619–2621, 2006
- [4] Update on Magnetic Resonance Imaging (MRI) Contrast Agents Containing Gadolinium and Nephrogenic Fibrosing Dermopathy, 2006. Available at: http://www.fda.gov/cder/drug/advisory/gadolinium_agents_20061222.htm. Accessed November 1, 2008
- [5] Parazella M, Current Status of Gadolinium Toxicity in Patients with Kidney Disease; *Clin J Am Soc Nephrol* 4: 461–469, 2009.
- [6] Janus et al. Prevalence of nephrogenic systemic fibrosis in renal insufficiency patients: Results of the FINEST study, *Eur Journal Radiol*. 2010; 73:357-359.
- [7] ACR committee on Drugs and Contrast Media, ACR Manual on Contrast Media, Version 9, 2013

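### Start of dialysis, a harm the protocol names, is not part of the Aim 1 renal outcome and is not systematically recorded after the 48-72 hour draw

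*Combined protocol and SAP*

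**What the plan says.** Hypothesis 1 (Hypothesis and Study Aims) concerns "adverse renal events, defined by decreased GFR and/or NSF". No threshold for a decrease is given, and dialysis is not listed.

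Under Study Design, Aim 1, each patient's "GFR will be recorded prior to the exams and 48-72 hours after scanning". Safety and Monitoring repeats this for renal toxicity: "Monitoring of this will be done by 48-72 hour post-exam serum creatinine evaluation". No later GFR is scheduled. For the longer term, "each patient will be contacted at baseline as well as 6 weeks, 3 months, and 6 months post-scan", and the stated purpose of those contacts is to look for NSF.

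Subject selection admits patients with "GFR less than 30 ml/min, but not on dialysis". Its GFR formula has serum creatinine in the denominator. Risks vs Benefits lists reduced renal function as a risk, "including the possibility of the need for permanent dialysis", together with NSF.

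Three other provisions bear on the point. The investigator and nurse coordinator track adverse events, which go to the IRB. The investigator reviews renal and NSF data every 3 months. Under Aim 2, related diagnoses and therapies are taken from the electronic medical record (EMR) for the study period and one year beyond it.

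**The concern.** Every patient enters off dialysis, so every start of dialysis during follow-up is a new event and among the most serious renal events the trial could see. The protocol tells patients it is possible but gives Aim 1 no means of counting it. Whether dialysis is permanent cannot be established by 72 hours, so the renal-function outcome cannot describe that harm at all.

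A second, narrower problem concerns direction. Dialysis removes creatinine (general knowledge, not stated in the documents). If it starts before the post-scan draw, the calculated GFR may rise. With no scoring rule, a patient with a severe renal event could be recorded as stable or improved, which favours the hypothesis.

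At stake is what this pilot can say about renal safety when it is used, as intended, to support a larger trial.

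**Working it through.** **1. The plan's own figure.** Statistics gives a reference rate of about 15%, an expected rate of at most 5%, 90% power, 5% significance and about 136 Gadoterate patients. A one-sample normal approximation against a fixed 15%, two-sided, with the null variance in both terms, gives

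(1.960 + 1.282)² × 0.15 × 0.85 / 0.10² = 134,

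within 2 patients of 136. The sample size therefore neither supports nor weakens the point. It does suggest that Aim 1 is a comparison of the Gadoterate event rate with 15%.

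**2. How the formula reads a creatinine drawn after dialysis.** The formula is eGFR = (140 − age) × kg × (0.89 if female) / (72 × creatinine). For an assumed 65-year-old man of 80 kg the numerator over 72 is 75 × 80 / 72 = 83.3. The creatinine values below are also assumed.

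| Creatinine (mg/dL) | eGFR | Reading |
|---|---|---|
| 4.0 | 20.8 | baseline |
| 5.5 | 15.2 | decrease |
| 2.5 after dialysis | 33.3 | 60% above baseline |
| 2.4 after dialysis | 34.7 | 67% above baseline |

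This is not automatic. If creatinine first rises by a factor r and dialysis then removes a fraction x, eGFR relative to baseline is 1 / [r(1 − x)]. The event is hidden only when x is at least 1 − 1/r: 20% for r = 1.25, 33% for r = 1.5 and 50% for r = 2. With r = 2 and x = 30% the ratio is 0.71, and the patient is still seen as a decrease.

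**3. When dialysis starts.**
- Before the 48-72 hour draw: the reading may be stable or improved, as in step 2.
- After the draw, with GFR already lower at the draw: the patient counts, through the GFR.
- After the draw, with GFR unchanged at the draw: Aim 1 misses the event. It is not reversed.

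**4. Effect on the Aim 1 rate.** The expected 5% is about 7 of 136, and each patient is 100/136 = 0.74 percentage points. The added events are an assumption; the documents give no dialysis rate. Intervals are exact, 95%, two-sided.

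| Events | Rate | 95% CI |
|---|---|---|
| 7 | 5.1% | 2.1-10.3% |
| 9 (2 added) | 6.6% | 3.1-12.2% |
| 11 (4 added) | 8.1% | 4.1-14.0% |

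For Aim 1 as measured, the added events would all have to be starts before the draw, that is 1.5% to 2.9% of the cohort within 72 hours.

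**5. Effect on the Aim 1 conclusion.** The protocol names no test. Assume an exact one-sided 5% test against 15% with n = 136: success is 13 or fewer events (actual level 4.3%). Counts of 9 and 11 both pass; from 7, it takes 14 − 7 = 7 more events to fail. The conclusion is more sensitive if the true rate is high. With a true rate of 15%, of which 1, 2 or 3 percentage points are dialysis cases scored as non-events, the chance of wrongly declaring a lower rate rises from 4.3% to 8.1%, 14.2% or 23.3%.

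**The case against.** A reader might infer that dialysis is never counted. The documents do not support that. A start could appear as an adverse event, in the 3-monthly review of renal data, or among related therapies in the EMR, and a patient whose GFR had fallen at a draw before dialysis counts already. What stands against these routes is that none is a defined count by cohort or feeds the Aim 1 analysis. The EMR record serves Aim 2 and does not name dialysis, and no renal data are scheduled after 72 hours for the review to cover.

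A reader might also infer a rule that scores dialysis as improvement, or one that removes patients who die or miss the draw. There is no such rule; the protocol is silent on all three. The improved-GFR case also needs dialysis within 72 hours in a patient who still has the research draw. Patients with hemodynamic instability or acute coronary syndrome, or with surgery or chemotherapy planned within 72 hours, are excluded. The case is narrow and probably uncommon.

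Nor is dialysis the first harm in Risks vs Benefits: it appears as a possibility within reduced renal function, which the trial does measure, though only early.

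Finally, starts months later may reflect the underlying disease in patients with GFR below 30, and the cohorts form partly by patient choice (Selection). A later comparison is therefore confounded. This limits how the added outcome may be read; it does not justify leaving it unrecorded.

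**Conclusion.** The gap is real and moderate. Aim 1 measures renal function once after the scan, at 48-72 hours. Start of dialysis is outside its event definition, is not systematically collected afterwards, and has no scoring rule if it comes before the draw.

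The size is unknown because the documents give no dialysis rate. It is tempting to conclude that uncounted dialysis would overturn the Aim 1 result. The figures do not show that: with an assumed 2 to 4 extra events the upper limits of 12.2% and 14.0% stay below 15%. The higher false-success risks in step 5 apply only if the true rate is as high as 15% and the hidden events start before the draw. The case for a change rests on reporting a harm the protocol itself names, at little cost.

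**What to change.** In the Aim 1 outcome definition, state that any start of dialysis before the 48-72 hour draw is an adverse renal event whatever the creatinine shows.

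At the existing 6-week, 3-month and 6-month calls, and in the planned EMR review, record whether and when dialysis started, in both cohorts. Report it by cohort with exact confidence intervals as a descriptive secondary renal safety outcome. State that the cohorts form partly by patient choice and that later starts may reflect underlying disease. If none of 136 patients starts dialysis, the one-sided 95% upper limit is 1 − 0.05^(1/136) = 2.2%, which is the most reassurance this outcome can give.

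The cost is one question at each of the three calls, one EMR field and one sentence in the outcome definition, with no extra draw, visit or patients. The downside is a possibly slightly less favourable event rate.
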